4.2 Exclusion Criteria

1. Pregnant or breastfeeding women;
2. Other malignancy within 5 years (except cured basal cell carcinoma, squamous cell carcinoma of skin, superficial bladder cancer, in situ carcinoma);
3. Anti-tumor therapy or participation in other clinical trials within 4 weeks before first study treatment;
4. Systemic corticosteroids ($> 10 \text{ mg}$ prednisone equivalent daily) or immunosuppressants within 14 days before first dose;
5. Grade ≥ 3 bleeding event within 4 weeks before screening, high bleeding risk, coagulopathy, anticoagulant use;
6. Uncontrolled cardiac disease (NYHA ≥ 2 heart failure, unstable angina, myocardial infarction within 1 year, significant arrhythmia, QTc $> 450 \text{ ms}$ (male)/ $> 470 \text{ ms}$ (female));
7. Severe comorbidities: active gastrointestinal bleeding, perforation, obstruction, severe infection;
8. Severe uncontrolled cardiovascular disease;
9. Active tuberculosis under treatment;
10. Prior anti-PD-1/PD-L1/PD-L2/CD137/CTLA-4 antibody therapy;
11. ECOG PS > 2 , hearing impairment, CrCl $< 50 \text{ mL/min}$, grade > 1 neuropathy;
12. Positive HCV RNA;
13. Any condition that may increase risk or interfere with study evaluation.

5. Study Design

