2.2 Risk–Benefit Assessment

Potential risks: immune-related adverse events (irAEs, such as pneumonitis, thyroid dysfunction), hypersensitivity, myelosuppression, surgical complications, etc.

Potential benefits: improved pCR rate, better swallowing and vocal function, reduced surgical trauma and complications, improved quality of life, prolonged survival.

Risk control: regular laboratory and imaging monitoring, laryngoscopy; adverse events

monitored according to NCI CTCAE 5.0; MDT dynamic evaluation of resectability.

3. Study Objectives and Endpoints

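### Exclusion 9 names active tuberculosis only when it is being treated, and the immune and hypersensitivity risks in 2.2 have no specific matching exclusion, so screening for both falls back on the unspecific item 13

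*Protocol*

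**What the plan says.** Section 4.2 of the protocol lists 13 exclusions. Five bear on this point:

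- Item 4 concerns recent medication: systemic corticosteroids above 10 mg "prednisone equivalent daily) or immunosuppressants within 14 days before first dose".
- Item 7 reads "Severe comorbidities: active gastrointestinal bleeding, perforation, obstruction, severe infection".
- Item 9 reads "Active tuberculosis under treatment".
- Item 10 removes anyone previously given a checkpoint antibody.
- Item 13 reads "Any condition that may increase risk or interfere with study evaluation".

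Section 2.2 states: "Potential risks: immune-related adverse events (irAEs, such as pneumonitis, thyroid dysfunction), hypersensitivity, myelosuppression, surgical complications, etc". The risk control that follows consists of laboratory and imaging monitoring, laryngoscopy, adverse event grading by CTCAE 5.0, and multidisciplinary review of resectability. Section 4.1 lists 11 inclusion criteria; its item 10 sets limits for blood counts, renal and hepatic function and coagulation.

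**The concern.** An eligibility criterion is applied as written. Item 9 joins two conditions, so a screener who follows the words excludes the patient whose active tuberculosis is being treated and finds nothing in that item against the patient whose active tuberculosis is not. That is unlikely to be what was meant in a trial of a PD-1 inhibitor.

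The second part is a mismatch within the document. Section 2.2 says which harms the sponsor expects. One would look in 4.1 and 4.2 for criteria that keep out patients already known to be prone to them. For myelosuppression there is such a criterion; for pneumonitis and the other immune-related events, and for hypersensitivity, there is none by name.

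At stake is patient safety, and also how uniformly the study population is selected. Exposure is not short: three neoadjuvant cycles, one or two more if the tumour is not yet resectable, and a year of maintenance for patients with a pathological complete response. With 10 patients, any single grade 3 or higher event moves that rate by 1/10 = 10 percentage points, so it matters whether the screening rule is clear.

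**Working it through.** No power, sample size or event calculation bears on this point. The check is a reading of all 11 + 13 = 24 criteria against section 2.2.

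**Step 1: tuberculosis.** Take each kind of patient with active disease and ask which criterion applies.

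| Patient | Item 9 (literal) | Item 7 | Item 13 |
|---|---|---|---|
| Active, being treated | excluded | if judged severe | arguable |
| Active, untreated, judged severe | not covered | excluded | arguable |
| Active, untreated, not judged severe | not covered | not covered | arguable |

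The third row is the gap. Only the general clause is left for that patient.

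**Step 2: risks in 2.2 against specific criteria.**

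| Risk named in 2.2 | Specific criterion in 4.1 or 4.2 |
|---|---|
| Myelosuppression | Yes: inclusion 10, blood count limits |
| Surgical complications | In part: inclusion 10 (coagulation) and exclusion 5 (bleeding) |
| Pneumonitis | None |
| Thyroid dysfunction and other immune-related events | None by disease; exclusions 4 and 10 act through medication history |
| Hypersensitivity | None |

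Counts over the 24 criteria: pneumonitis or interstitial lung disease, 0; autoimmune disease, 0; hypersensitivity, 0; tuberculosis, 1 (item 9).

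**Step 3: what item 4 does.** It excludes on what the patient has taken in the last 14 days. Someone with autoimmune disease who takes no immunosuppressant, and at most 10 mg prednisone equivalent a day, passes it. So does someone with past pneumonitis who is no longer on steroids.

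**Step 4: what item 13 does.** It can reach every patient in steps 1 to 3, because it covers whatever may raise risk. But it names no condition, sets no threshold and does not say who decides. It therefore prevents the statement that these patients are eligible, and it does not make their exclusion predictable.

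**The case against.** The strongest reply is that item 13 already excludes these patients. Its wording is not qualified by anyone's opinion, and untreated active tuberculosis or a known severe hypersensitivity would be hard to describe as anything other than a condition that may increase risk. Item 7 adds severe infection, item 4 removes anyone on an immunosuppressant at any dose, and item 10 removes anyone with earlier checkpoint exposure. Item 9 may simply be loose drafting or translation. All of this stands, and it limits the point: nobody here is admitted by rule. It does not remove it. If item 13 were enough, most of the specific exclusions would be unnecessary, and a specific item that mentions only treated disease invites the reading that untreated disease was left out on purpose.

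Several stronger readings are tempting but not supported:

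- A reader might infer that patients at the highest risk of immune toxicity are eligible. Item 13 contradicts the second half, and the protocol has no figure or statement that ranks patients by risk.
- A reader might tie tuberculosis or autoimmune disease directly to the list in 2.2. That list names neither; the link to autoimmune disease is an inference from the immune-related events, and the tuberculosis point rests on the wording of item 9 alone.
- A reader might add hepatitis B, since the viral hepatitis item reads only "Positive HCV RNA". Section 2.2 does not mention hepatitis, inclusion 10 caps bilirubin and transaminases, and item 13 applies here too. The document does not carry that claim.
- A reader might say that one such patient costs 10 points of the pCR rate. That holds only if the patient would have had a complete response and is then counted as a failure; the protocol supports neither assumption.
- A reader might say that risk control is only monitoring after dosing. Section 2.2 does not limit monitoring to that period, and section 5.3 collects baseline imaging and laboratory data. What can be said is that none of the measures in 2.2 is a rule for selecting patients.

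**Conclusion.** The point holds in a limited form. Item 9 is miswritten: on its literal reading, untreated active tuberculosis is outside the one criterion that names the disease and is reached only by item 7, when severe, or by item 13. Separately, the pneumonitis, other immune-related and hypersensitivity risks in 2.2 have no specific counterpart among the 24 criteria, so screening for predisposed patients rests on item 13.

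The size is one criterion to correct and three conditions not named. How many patients would be affected cannot be derived from the protocol, and no effect on the pCR or adverse event rates is claimed. The conclusion assumes that criteria are applied as worded and that no screening manual or checklist outside the protocol already settles these cases. It should be put right because the correction is cheap and concerns patient safety; it does not call the design or the endpoint into question.

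**What to change.** Reword item 9 so that it covers active tuberculosis whether or not it is under treatment. Ask the sponsor to reconcile 4.2 with 2.2 by adding specific exclusions that match the listed risks: immune-related disease, pneumonitis or interstitial lung disease, and hypersensitivity to components of the study drugs. The sponsor should set their terms, including look-back periods and any exceptions; this review proposes none. Item 13 can stay as the general clause.

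The cost is a short protocol amendment and an updated screening checklist. If the sponsor wants chest imaging for the lung criterion, the protocol should say so: section 5.2 specifies neck imaging for response, and section 5.3 lists baseline imaging without naming a region. A few candidates may be excluded, which could slow enrolment of 10 patients over the planned 12 months; the documents do not allow that number to be estimated.

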5.1 Overall Design

Prospective, single-arm, single-center study.

Sample size: 10 patients.

Planned enrollment period: 12 months.

Follow-up period: 5 years.

5.2 Intervention

Phase	Intervention
Neoadjuvant combination	Vibecortamab 2.0 mg/kg IV infusion 60±10 min q3w; Putilimab 200 mg IV infusion 40±10 min q3w; 3 cycles total
Imaging assessment	Enhanced neck CT/MRI 3–4 weeks after cycle 3; RECIST 1.1
Surgery	Radical resection + neck dissection within 4 weeks; laryngeal function preservation as much as possible
Postoperative adjuvant	pCR: maintenance for 1 year; MPR: standard adjuvant; high-risk: radiotherapy/chemoradiotherapy

5.3 Data Collection

- Baseline: demographics, clinical features, pathology, imaging, laboratory tests;
- Treatment-related data: dosage, cycles, AEs (CTCAE 5.0), imaging response (ORR = CR+PR);
- Efficacy: residual tumor percentage, margin status, pCR/MPR;
- Follow-up: swallowing (EAT-10), vocal function (VHI-13), quality of life (UW-QOL, VAS), survival (DFS, OS).

